#### 8.3 Secondary outcome statistics

To evaluate the effect of the StepIt exercises on lymphoedema control in the control group will be compared with data from the StepIt group. The StepIt exercise data will be stratified into different groups according to coherence to treatment.

Efficacy is defined by the following parameters:

- Leg volume (indirect via circumference measurements)
- Ankle circumference
- Ankle range of motion

- Visual analogue pain score
- Quality of Life questionnaires scores

To compare the groups in terms of leg volume and ankle circumference, Mann-Whitney U-test or ttest will be applied , depending on distribution of data.

To assess ankle range of motion, the average differences between first and last visit will be calculated. The control and intervention group will be compared by applying Mann-Whitney U-test or unpaired t-test depending on the distribution of the data.

To measure patient-reported outcome measures on quality of life at first visit, second visit and final visit, the Mann-Whitney U-test will be performed. Data of the control and intervention group will be compared by applying the Mann-Whitney U-test.

Subject to sufficient data being available, Cox proportional hazards regression analysis will be conducted to investigate the role of StepIt and other covariates in leg lymphoedema symptom control. Other covariates include: lymphoedema severity and chronicity at baseline, ankle motion range, patient age, patient mobility, absence/presence of co-morbidities.

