#### 4. STUDY HYPOTHESIS

#### 4.1 **Primary objective**

• To assess the feasibility of conducting a full RCT in the future

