#### 6. SUBJECTS

#### 6.1 Anticipated number of research subjects

This concerns a feasibility trial, and therefore the results from this study should inform a potential effect size for StepIt pedal exercise therapy, and also the degree in variance in lymphoedema volume changes (primary clinical outcome). To date, there is not sufficient published data to gain an insight in the effect that calf muscle exercise may have on lymphoedema symptoms. Guidance from a publication by Julious (2005) advises the use of 12 participants per treatment arm, and this approach will be taken here (see Table 5). Patient withdrawal rates before week 12 are not known at present and measuring this will be a primary aim

Table 5, sample size numbers required, based on hypothetical differences between published data and study outcomes

	Standard (control) arm	care	Standard care plus Steplt pedal arm
Patients (n)	12		12

Since this concerns a randomised controlled trial, albeit in the shape of a feasibility study, reprting will be done in line with CONSORT guidelines (Schulz, Altman & Moher 2010). The number of patients screened but who did not meet the inclusion criteria or who declined to participate will be recorded, as will any patients who are lost to follow-up (Appendix 2).

The patient attrition rate (withdrawal and loss to follow-up) will also be recorded, since this involves a study with at multiple visits, albeit incorporated into standard clinical appointments. Patients will be recruited from the adult (age 18+) population routinely seen by the evaluating clinical staff members.

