#### 6.1.1 Randomisation

A 1:1 allocation to the control and intervention group respectively will be applied. Following written consent patients will be allocated at random to the control or intervention group, using a non-restricted randomised sequence generated for the whole sample using a free ware randomisation programme, see https://www.randomizer.org/. Sequential envelopes with each next randomisation allocation will be used to achieve concealment.

The researcher/lymphoedema care specialist will inform the patient what arm they have been allocated. As the study involves the Clinical Lymphoedema Specialist or Researcher consenting and following up patients and a self-administered intervention of necessity it is not possible to achieve blinding for the participants or the Clinical Lymphoedema Specialists.

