#### 8.2 **Primary outcome statistics**

The primary objective for this pilot study was the feasibility of conducting a larger scale randomised controlled trial. The secondary outcome statistics are other clinical and patient related outcomes measures.

The following descriptive statistics will be reported on:

- Number of patients screened
- Number of patients eligible/ineligible, and percentage of patients consented into the trial
- Number of patients completed the trial/discontinued (plus reasons if discontinued)

Lymphoedema control: Mann-Whitney U-test of change in leg volume (week 0 vs 12) between control and StepIt groups respectively.

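### Leg volume has two different stated analyses and quality of life is tested without its baseline; one baseline-adjusted estimate would serve the purpose in section 6.1 better

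*Protocol*

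**What the plan says.** **Leg volume.** Sections 2.1 and 6.1 name leg volume as the primary clinical outcome. Section 8.2 specifies a "Mann-Whitney U-test of change in leg volume (week 0 vs 12) between control and StepIt groups respectively". Section 8.3 returns to it: "To compare the groups in terms of leg volume and ankle circumference, Mann-Whitney U-test or ttest will be applied", with the choice left to how the data turn out to be distributed. Section 8.3 does not say whether absolute volume or change is compared, or at which visit.

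**Quality of life.** Section 8.3: "To measure patient-reported outcome measures on quality of life at first visit, second visit and final visit, the Mann-Whitney U-test will be performed". A separate sentence then says that the two arms will be compared with the same test. Neither mentions a change score or a baseline term. EQ-5D-5L and LYMQOL are collected at weeks 0, 6 and 12 (section 5.3, Table 3; section 5.5.2).

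**Purpose.** The primary objective in section 4.1 is feasibility: "To assess the feasibility of conducting a full RCT in the future". Section 6.1 adds that "the results from this study should inform a potential effect size for StepIt pedal exercise therapy, and also the degree in variance in lymphoedema volume" change. The sample is 12 per arm by a rule of thumb: the cited guidance "advises the use of 12 participants per treatment arm, and this approach will be taken here".

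**The concern.** Three things are fixed badly in the current text.

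1. The primary clinical outcome has two analysis rules, one of them dependent on the data. An analyst could follow either and claim to have followed the protocol.
2. The quality-of-life analysis leaves out a baseline that every participant supplies. With about 12 per arm, chance baseline differences are sizeable and carry through into the follow-up comparison.
3. The clinical analyses are stated as tests. A Mann-Whitney p-value is neither an effect size nor a variance, and the descriptive statistics listed in section 8.2 cover only screening, eligibility and consent, and completion.

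At stake are the clarity of the leg-volume result, the precision of the quality-of-life comparison, and whether the pilot reports the quantities that section 6.1 mentions.

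**Working it through.** **No stated figure to reproduce.** The protocol gives no power, effect size or SD. Its 12 + 12 = 24 is consistent with the summary.

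**Leg volume, the two sections side by side**

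| | Section 8.2 | Section 8.3 |
|---|---|---|
| Test | Mann-Whitney | Mann-Whitney or t-test, chosen from the data |
| Quantity | Change | Not stated |
| Time point | Week 0 to 12 | Not stated |

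**Quality of life, the two readings.** Let r be the correlation between a person's baseline and follow-up values, with equal SDs at both visits.

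- *Arms compared at each visit.* At the first visit any true difference is zero by randomisation, so that test can detect only chance.
- *Visits compared within people.* The separate sentence on comparing arms makes this reading plausible. Mann-Whitney assumes independent samples. The variance of the mean visit difference is proportional to 2(1 - r), but an independent-samples analysis takes it as 2, which is 1/(1 - r) times too large: 2.0 times at r = 0.5 and 3.3 times at r = 0.7.

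**Inputs for precision.** n = 12 per arm (section 6.1); 1:1 allocation (section 6.1.1). Assumed, because the documents give no figure: two-sided 5%, and r over the range shown.

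**Chance imbalance.** SE of the baseline difference = sqrt(2/12) = 0.41 SD. An unadjusted follow-up difference carries r times the imbalance. For an imbalance of one SE this is 0.5 × 0.41 = 0.20 SD to 0.7 × 0.41 = 0.29 SD.

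**Relative variance of the between-arm difference**

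- Follow-up score alone: 1
- Change score: 2(1 - r)
- Baseline-adjusted: 1 - r², times 1 + 1/(2n - 4) = 1 + 1/20 = 1.05 for estimating the slope

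95% CI half-width = t × sqrt(relative variance × 2/12), with 22 df for the first two (t = 2.074) and 21 df for the adjusted analysis (t = 2.080). For follow-up alone this is 2.074 × 0.408 = 0.85 SD.

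| r | 1 - r² | Half-width, follow-up | Half-width, change | Half-width, adjusted |
|---|---|---|---|---|
| 0.5 | 0.75 | 0.85 | 0.85 | 0.75 |
| 0.7 | 0.51 | 0.85 | 0.66 | 0.62 |
| 0.8 | 0.36 | 0.85 | 0.54 | 0.52 |
| 0.9 | 0.19 | 0.85 | 0.38 | 0.38 |

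With the 5% cost included, the variance against follow-up scores is 0.75 × 1.05 = 0.79 at r = 0.5 and 0.51 × 1.05 = 0.54 at r = 0.7. Against change scores the ratio is (1 + r)/2 × 1.05: 0.945 at r = 0.8 and 0.998 at r = 0.9. The gain is then close to nil.

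**Precision of the SD.** With 22 df the 95% limits are sqrt(22/chi-square) = 0.77 to 1.42 times the estimate.

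**Why the correlation is worth reporting.** For illustration, a later trial with 80% power at 0.5 SD (both assumed) needs, per arm, for follow-up / change / adjusted analysis: 63 / 63 / 48 at r = 0.5 and 63 / 26 / 23 at r = 0.8.

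**The case against.** The strongest reply is that this is a 24-person feasibility trial in which efficacy is secondary, and that estimates, intervals and model form are commonly left to an SAP, which may exist. That stands as far as missing detail goes. It does not remove the two rules for leg volume or the quality-of-life sentence, because the protocol states both.

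A reader might infer more than the documents support:

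- *That the planned analyses cannot yield an effect size or variance.* The t-test branch rests on a mean difference and pooled SD, and SDs can be tabulated beside any test. The defect is that estimates are not named.
- *That the trial exists to supply those figures.* Feasibility is primary; section 6.1 gives this as one use of the results.
- *That baseline is ignored throughout.* Section 8.2 uses change for leg volume, and section 8.3 uses first-to-last-visit differences for ankle range of motion. The point is confined to quality of life.
- *That the main trial will be sized on the pilot's effect.* The protocol does not say so, and section 6.1 needs no rewrite on that account.

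It is also fair that Mann-Whitney is one of the two options in section 8.3, so one clarification would settle the leg-volume conflict. The quality-of-life items are ordinal, so a rank test is defensible. That supports keeping it as a check; it does not justify leaving baseline out.

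**Conclusion.** The point holds in limited form. Sections 8.2 and 8.3 need reconciling for leg volume, and the quality-of-life sentence is faulty on either reading. A baseline-adjusted difference with its CI is a better analysis than the one stated and uses data already collected.

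The benefit is clearest for quality of life: variance about 75% to 51% of that from unadjusted follow-up scores at r = 0.5 to 0.7, or 79% to 54% after the small-sample cost. For leg volume the benefit over change scores is small if r is about 0.8 or more. There the case rests mainly on having one rule and reported estimates.

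The contradiction and the unused baseline can be read directly from the text. The sizes rest on assumed correlations, equal SDs at both visits and all 12 per arm contributing. Adjustment does not make the estimate precise: even at r = 0.7 the half-width is 0.62 SD.

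**What to change.** Amend sections 8.2 and 8.3 as follows:

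- State one analysis for leg volume in both sections. For this and the other continuous or score outcomes, regress the follow-up value on arm and the same measure at baseline. Use one value per participant, since section 6.2.1 admits disease in one or both legs.
- Report the adjusted difference with 95% CI, the SD of week 0 to 12 change, the SD at follow-up, and the baseline-to-follow-up correlation.
- Keep Mann-Whitney on change as a sensitivity check, and remove the choice of test from the observed distribution.
- Drop the between-arm test at the first visit, and reword the quality-of-life sentence so that it is clearly a comparison of arms using baseline.

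**Cost.** Wording only; the baselines are already scheduled in Table 3. The downside is a model assumption at about 12 per arm, which the rank-test check covers.

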## **RESEARCH PROTOCOL SUMMARY**

TITLE:	PEDAL; Plantar Exercise, Daily, for Lymphoedema, a single- centre, controlled, prospective, randomized feasibility trial			
Short title:	PEDAL trial			
IRAS number	265968			
Device description Study design	StepIt plantar flexion rocker pedal device. CE-marked and licensed medical device. To be used in this study for indicated purpose, namely plantar flexion exercise.Multi centre, controlled, prospective randomized feasibility			
	trial			
Primary objective	To assess the feasibility of conducting a full RCT in the future			
	
 
Participants' compliance to StepIt exercise regime and total number of steps achieved
 
Recruitment and attrition rates, willingness of patients to be randomised, response rates to questionnaires, and degrees of missing data
 
Testing of eligibility criteria and ability/willingness of clinical staff to partake in recruitment of participants
 
Adequacy of duration of follow-up (e.g. in relation to lymphoedema status)
 
			
Secondary objectives	To determine the acceptability and efficacy of the step-it pedal as an adjuvant therapy for leg lymphoedema at 6 and 12 weeks post-baseline			
	
 
Efficacy of StepIt pedal adjunct therapy vs standard care. Status leg volume difference.
 
Ankle circumference
 
Ankle range of motion
 
Lymphoedema-related quality of life
 
General quality of life
 
Patient feedback on use of the device (StepIt users only)
 
			
Patient population	A total of 24 participants, over the age of eighteen, with leg lymphoedema managed by the community lymphoedema team. Participants must have the capacity to provide informed written consent and complete patient reported outcome measures. Participants are recruited from the local Hospice at Home lymphoedema service caseload.			

	
 
12 Patient will receive treatment as usual (TaU)
 
12 Patients will receive TaU plus StepIt exercise programme intervention
 
			
	Randomisation will not be stratified.			
Sponsor	North Cumbria Integrated Care NHS Foundation Trust			
Manufacturer & funder	StepIt System AB, [name] Contact: [name], PhD, [contact]			
	[contact]			
Chief Investigator	[name], GPwSI Research, North Cumbria Integrated Care NHS Foundation Trust, R&D Department, [name] [contact]			
Co-investigators				

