#### 5.5.2 Secondary outcome measures

The primary outcome for this pilot trial will be the feasibility of conducting a full RCT in the future. However, this study also aims to provide preliminary results regarding the acceptability and efficacy of a simple StepIt pedal as an adjuvant therapy for lymphoedema symptom control.

Clinical outcome measures

- Leg volume (see notes below), at week 0, 6, 12
  - Measured only between 9.30am to 3.30pm
  - Where possible the same rater is used for each participant; name of rater will be recorded.
- Ankle circumference measurement, using lateral malleolus as reference point (Brodovicz et al, 2009), at week 0, 6, 12
- Clinician's oedema severity score (Table 4 below; Nieman et al, 2013)

Table 4.	Clinician's	oedema	severity	/ score
TUDIC T,	chinciun 5	ocucina	JUVUII	, 20010

	0	1+	2+	3+	4+
Visible	No	yes	yes	yes	yes
Pitting	No	slight	>slight	>slight	'can't reach tibia'
Level	n/a	n/a	< knee	>knee	>knee

- Ankle range of motion (using goniometer)
- Pain score, at week 0, 6, 12
- Quality of life score, determined with EQ-5D-5L and LYMQOL-L Questionnaire, at week 0, 6, 12
- Participant opinion on trial participation, at week 12 (StepIt users only)
- Patient withdrawal rates due to change in management (e.g. need for surgery, hospital admission, infection, or other)
- Leg infection rates, primarily cellulitis

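### Section 8.3 plans a Cox model for lymphoedema symptom control, but the protocol defines no event for that model to analyse

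*Protocol*

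**What the plan says.** The Cox model appears once, at the end of Section 8.3: "Cox proportional hazards regression analysis will be conducted to investigate the role of StepIt and other covariates in leg lymphoedema symptom control". It is introduced by the condition "Subject to sufficient data being available", with no threshold for what counts as sufficient. The covariates besides StepIt are "lymphoedema severity and chronicity at baseline, ankle motion range, patient age, patient mobility, absence/presence of co-morbidities".

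The rest of the protocol treats lymphoedema control as a quantity measured at fixed visits:

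- Section 8.3 defines efficacy by five parameters: leg volume, ankle circumference, ankle range of motion, visual analogue pain score and quality-of-life scores.
- Section 5.5.2 sets the main clinical measure as "Leg volume (see notes below), at week 0, 6, 12". Table 3 in Section 5.3 gives the same three visits for the other efficacy measures, except ankle range of motion, which is taken at weeks 0 and 12 only. The week 6 and week 12 visits may each be up to two weeks early or late.
- Section 8.2, under the label of lymphoedema control, specifies a Mann-Whitney test of the change in leg volume from week 0 to week 12.

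The sample is small by design. The summary gives "A total of 24 participants, over the age of eighteen, with leg lymphoedema managed by the community lymphoedema team", and Section 6.1 cites guidance that "advises the use of 12 participants per treatment arm, and this approach will be taken here".

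**The concern.** A Cox model needs an event, a point from which time is counted and a rule for when observation stops. Section 8.3 names the model and its covariates but supplies none of these for symptom control. An analyst who had to run it would first have to invent a responder definition, such as some percentage fall in leg volume, after the data had been collected. That choice would be arbitrary, would discard most of the information in a continuous measurement, and could move the result.

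This is also the only covariate-adjusted effect of StepIt that the protocol plans. Section 6.1 says the trial should inform an effect size and the variance of leg-volume change for a later trial. A hazard ratio for an improvised event gives neither.

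**Working it through.** **1. Is there an event for the model?** Setting the sections side by side:

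| Place | How lymphoedema control is treated | Type of data |
|---|---|---|
| 8.2 | Change in leg volume, week 0 to 12, compared between arms | Continuous |
| 8.3, efficacy parameters | Volume, circumference, range of motion, pain, quality of life | Measurements and scores |
| 8.3, last paragraph | Outcome of a Cox model | Needs an event and a time; neither is defined |

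The protocol gives no figure for this analysis to reproduce: no event count, event rate, hazard ratio or power.

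**2. Could the visit schedule supply event times?** An event derived from the efficacy measures could be detected only at the week 6 or week 12 visit. With the two-week allowance these visits fall in weeks 6 − 2 = 4 to 6 + 2 = 8, and 12 − 2 = 10 to 12 + 2 = 14. Recorded times within those windows would reflect appointment dates. The true time would be known only to lie between one visit and the next, so the data would be interval-censored with two inspection times, or one for range of motion. In nominal visit time almost all events would be tied.

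**3. How much information would there be?**

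Inputs: N = 24 (Summary; Section 6.1), allocation 1:1 (Section 6.1.1), six named covariates plus StepIt (Section 8.3). Assumptions, because the protocol does not say: all seven terms enter one model with one coefficient each, and the event proportion is unknown, so a range is shown. Detectable hazard ratios use two-sided alpha 0.05 and 80% power.

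Events per coefficient = d / 7, where d is the number of events. Detectable HR = exp[(1.960 + 0.842) / √(d/4)].

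| Events d | Share of 24 | d / 7 | HR detectable with 80% power |
|---|---|---|---|
| 24 | 100% | 3.4 | exp(2.802/2.449) = 3.14 |
| 12 | 50% | 1.7 | exp(2.802/1.732) = 5.0 |
| 6 | 25% | 0.9 | exp(2.802/1.225) = 9.9 |

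In the other direction, Schoenfeld's formula, d = 4(1.960 + 0.842)² / (ln HR)², requires 66 events for HR 2 and 27 for HR 3. Both exceed 24. These formulas ignore the cost of estimating six further coefficients, so they are optimistic.

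**4. What would such a model return?** A simulation with no true treatment effect (2,000 runs per scenario; 12 against 12 participants; events seen only at weeks 6 and 12; seven coefficients; Efron handling of ties) gave these central 95% ranges for the estimated treatment hazard ratio:

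- 75% of participants with an event: 0.27 to 3.7
- 50% with an event: 0.14 to 6.6
- 25% with an event: 0.03 to 43, and a further 20% of fits failed or separated

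The type I error was 6–7% in the first two scenarios, modestly above the nominal 5%. Small numbers and ties therefore mainly cost precision. The absent event in step 1 is a different kind of fault: it leaves the analysis unspecified.

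**The case against.** The strongest defence is that the analysis is conditional on sufficient data and comes last among the secondary analyses of a feasibility trial. With too few events the condition would stop the model being run. That answers much of the sample-size argument, although the condition has no threshold. It does not answer the missing event, because the condition concerns quantity and no quantity of leg-volume readings becomes a time to event without a definition. Nor is this a detail that can simply be left to a statistical analysis plan, since the protocol itself fixes a model class that does not match its outcomes.

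Four stronger readings are tempting, and the protocol does not support them:

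- *The trial has nothing that could be timed.* Section 5.5.2 lists leg infection and withdrawal due to a change in management, and Section 6.3 records suspensions of the exercises. These could be dated in principle. But infection and withdrawal are listed as rates, and the Cox model is aimed at symptom control, not at any of them.
- *Two visits and 24 participants make any Cox result invalid.* The simulation shows severe imprecision with only modest type I error inflation in the 50% and 75% scenarios. Interval-censored data can be analysed once an event exists.
- *Seven coefficients are certain.* Section 8.3 lists covariates without saying that all enter together. They might be examined singly, so the 3.4 and 1.7 figures depend on the joint-model reading.
- *Patient mobility is not collected at baseline because Section 8.1 omits it.* The EQ-5D-5L is completed at week 0 (Table 3) and its first item is mobility (Appendix 1). Section 8.1 is not a full list of baseline data, since it also omits ankle range of motion, which is measured at week 0.

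**Conclusion.** The point stands in a limited form. The Cox model in Section 8.3 does not fit its stated target, because symptom control has no event, time origin or censoring rule and is otherwise treated as a measurement. This conclusion comes from the text alone and needs no assumption about numbers.

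The imprecision is secondary. It rests on an assumed joint model with seven coefficients and on assumed event proportions.

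Severity: should fix. The analysis is conditional and secondary. The feasibility objective, the Section 8.2 comparison of leg volume, randomisation and data collection are all unaffected. A reader might infer that the trial's efficacy analysis as a whole is unsound, but the separate two-group comparisons in Sections 8.2 and 8.3 do not depend on the Cox sentence.

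**What to change.** Delete the Cox sentence and its covariate list from Section 8.3. Deletion alone removes the inconsistency.

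If a covariate-adjusted estimate is wanted, replace it with wording such as: *As an exploratory analysis, leg volume at week 12 will be analysed by a linear model (ANCOVA) with treatment arm and baseline leg volume, and at most one further baseline covariate named in advance (for example lymphoedema severity). The adjusted mean difference will be reported with a 95% confidence interval. Other covariates will be summarised descriptively by arm.* With complete data and a single-coefficient covariate, this model estimates four parameters (intercept, arm, baseline volume, one covariate) and leaves 24 − 4 = 20 residual degrees of freedom. It yields an effect estimate and a residual variance on the leg-volume scale, which is what Section 6.1 asks the trial to inform.

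The linear model is one reasonable choice; the necessary step is to remove the mismatch. If the investigators do want a time-to-event analysis, they would have to define the event, time origin and censoring rule in advance and use a method for interval-censored data. With 24 participants it would remain very imprecise.

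The cost is a wording change in Section 8.3. No new data or visits are needed. Because Section 10.1 bars departures from the protocol without prior review and approval, the change should go through as an amendment before analysis.
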